### Cost effectiveness analysis:

Cost data relating NHS resource use (in both primary and secondary care) will be collected following established methods [44] up to 3 months post-termination for both surgical and medical interventions. This will include data relating to the initial procedure, hospital stay, follow up care as inpatients, any additional interventions and out-patient appointments. Data relating to GP consultations specifically for follow up care relating to the TOP will be collected using the postal questionnaire at 3 months and, if agreed previously, by telephone where this is not returned. Data relating to secondary and primary follow up care and any interventions required will be used to compare the burden placed on patient own resources when using either medical or surgical termination. The cost-effectiveness analysis will be expressed as the cost per successfully completed termination. Extensive one-way and multivariate sensitivity analysis will be undertaken in the analysis of the final results [45].

### Clinical effectiveness analysis:

Previous studies have used a variety of measures of clinical effectiveness but emphasis has been placed on failed TOP (with an ongoing viable pregnancy), incomplete abortion and presumed pelvic infection. Based on our proposed sample size, the precision with which we could detect differences in each of these complications is limited. Hence we have opted to use a combined measure of effectiveness which captures unplanned time spent in hospital, a key outcome for women.

Our definition of 'emergency admission' includes;

- 1. Unplanned overnight stay on the day of termination
- 2. Emergency hospital assessment or admission after discharge

All cases of incomplete abortion, missed abortion, ongoing pregnancy (all of which require surgical evacuation) and pelvic infection without retained products of conception will therefore be included in this outcome. A very small number of women may be admitted to other units but we would anticipate collecting clinical outcome data from their hospital discharge summary and/or via our follow up.

#### Qualitative sub-study

Conjoint analysis or discrete choice experiment (DCE):

In order to identify the key factors that shape women's preferences for termination services we will conduct a discrete choice experiment. This technique measures the strength of individual's preferences for the various attributes of a clinical intervention [46] and has been successfully used in research relating to the provision of services for women [47]. Interviews will be conducted with a sample of 100 non-pregnant women recruited from local Contraception / Sexual Health clinics. Women will first be asked if they are interested in participating in a research interview, before provision of an information sheet, an informed discussion and written consent. These interviews will begin prior to recruitment for the main study. Previous research suggests this sample size should be adequate to provide precise parameter estimates with the number of attributes and choices we will use [48]. This sampling frame has been chosen to reduce the data collection burden on the trial sample and to avoid interference with women in the trial forming and stating preferences.

#### Qualitative analysis:

We will use a model of preference developed from the discrete choice experiment as the basis for a semi-structured interview with 32 women (8 from each of the four groups: preference

surgical, preference medical, randomised surgical and randomised medical). A conventional model of qualitative analysis will be used [49]. The analytic product of this work will be (1) a comparative model of preferences and their normative constraints and (2) a model of contextual features that affect decision-making about termination of pregnancy.

Interview transcripts will form the formal data for analysis. Following the conventional model of constant comparative analysis of transcribed data set [49], transcripts will be interpreted iteratively, developing themes (or categories) within respondents' discourse. To facilitate qualitative analysis, and to provide an audit trail for governance purposes, we will use QSR software to manage data transcripts, coding and memo'ing. Initial thematic analysis will be conducted by the qualitative researcher. Transcripts will be searched for common themes and deviant cases (in relation to part 1 of the interview). Themes will be indexed (as 'codes') and searches for discrete instances of codeable items of speech will be undertaken in both cumulative comparisons (i.e. between interviews in the same arm of the trial) and condition comparisons (i.e. across interviews gathered from different arms of the trial). This will provide a robust account of the common themes relating to women's responses of joining and participating in the trial, and these themes (and deviant cases) will be recorded in a simple frame [50]. Because part 2 of each interview will involve some structured questions (and flashcards showing simple histograms of quantitative data), direct thematic comparisons will be made across a range of responses, and some simple quantification of results will also be possible. Once initial analysis have been undertaken by the qualitative researcher, qualitative inter-rater checking will be undertaken on a sample of cumulative and condition comparisons. This will add value to analysis [51] and will enable secure claims about the quality of data to be made.

# **15.2 Sample size calculation**

The power of the study is based on the main comparison of acceptability between women randomised to medical or surgical TOP. Assuming the acceptability of medical termination to be 75%, we would need responses from 335 women in each randomised arm to detect a difference in acceptability of 10% (i.e. from 75% to 85%) with a significance level of 5% and power of 90%. We believe this difference in the level of acceptability is important for both consumers and providers; a similar difference was employed by Ashok et al [15] in their large randomised comparison of abortion methods.

Based on the power calculation we need primary outcome data on 670 women randomised to medical or surgical TOP at <14 weeks' gestation. In order to achieve this number we calculated;

- 1. 1116 women need to be randomised (assuming 40% of women randomised fail to attend for follow up and primary outcome data is therefore not available).
- 2. 2232 women need to be recruited (assuming 50% of women agreeing to participate in the study have a preference for medical or surgical TOP and are therefore not suitable for randomisation).
- 3. 3188 women need to be approached (assuming 30% of women accepted for TOP will decline involvement in the study).

Justification for assumptions – All three assumptions were based on our experience from an earlier pilot trial conducted at the RVI involving women requesting TOP at 9-13 weeks' gestation. For reasons detailed in [25] we believe our assumption of 60% follow up is conservative. Further, previous trials conducted in the UK have reported that 54% [14] and 82% [15] of recruited women undergoing TOP at < 9 weeks and 9-13 weeks respectively were prepared to have their method of TOP determined by randomisation. Thus our estimate of 50%

# **16** COMPLIANCE AND WITHDRAWAL

In order to increase the proportion of participants returning for follow up after 2 weeks, an option to attend a community clinic has been incorporated in the design. Thus, allowing ease of access and evening appointments.

A range of contact processes are also included to maximise capture of primary and secondary data where participants fail to attend the week 2 follow up visit. These include telephone contact (up to three attempts), postal questionnaires (up to two attempts), or a web-based questionnaire option, to capture the primary variable. For agreeable participants text messaging will be used for a visit reminder at week 2 and collection of the primary variable (up to two attempts).

Following reasonable attempts to capture data and non-response, participants will be considered lost to follow-up.

Participants who withdraw their consent following the procedure will not be replaced.

# **17 DATA MONITORING**

# **17.1 Discontinuation rules**

The trial may be prematurely discontinued on the basis of new safety information, or for other reasons given by the Trial Steering Committee (see below), regulatory authority or ethics committee concerned.

# 17.2 Monitoring, quality control and assurance

The trial will be managed through the Clinical Trials Unit (CTU), University of Newcastle in accordance with the EU Trials Directive, the Research Governance Framework for Health and Social Care and MRC Guidelines for Good Clinical Practice in Clinical Trials. [name] will have overall responsibility for the day to day conduct of the trial supported by the nurse coordinator, CTU Trial Manager and Trial Management group (TMG). The TMG will include the principle investigators, co-applicants and nurse representation.

The Trial Steering Committee (TSC) will be chaired by [name], University of Aberdeen, to include two other independent members and two lay members. It is proposed the TSC will meet twice during the first year of the trial and then annually. Their role is to monitor and supervise the trial, to ensure it is conducted to high standards in accordance with the protocol, the principles of GCP, and with regard to patient safety.

The Trial Manager will ensure that the study is conducted in accordance with GCP through a combination of central monitoring and site monitoring visits.

Central monitoring

• all documentation essential for study initiation will be reviewed prior to site authorisation

Site monitoring

• Consent forms will be reviewed as part of the study file and the presence of a copy in

medical records confirmed

- Consent forms will be compared against the study participant identification list
- Inclusion/exclusion criteria will be reviewed for 20% of participants
- Serious adverse events will be verified against medical records
- The presence of essential documents in the study file will be checked
- Management of the IMP will be reviewed periodically

All monitoring findings will be reported and followed up with the appropriate persons in a timely manner.

A final site visit will be performed at the end of the study

- To complete final monitoring requirements, as above
- To review archiving of study site documentation

# **18 PHARMACOVIGILANCE**

### **18.1 Definitions**

An 'adverse event' (AE) is any untoward medical occurrence which does not necessarily have a causal relationship with the treatment.

A 'serious adverse event' (SAE) is any untoward medical occurrence or effect that at any dose

- results in death,
- is life-threatening,
- requires hospitalisation or prolongation of existing inpatients' hospitalisation,
- results in persistent or significant disability or incapacity.

Life-threatening in the definition of a serious adverse event or serious adverse reaction refers to an event in which the subject was at risk of death at the time of the event; it does not refer to an event which hypothetically might have caused death if it were more severe.

Medical judgement should be exercised in deciding whether an adverse event or reaction is serious in other situations. Important adverse events or reactions that are not immediately life-threatening or do not result in death or hospitalisation but may jeopardise the subject or may require intervention to prevent one of the other outcomes listed in the definition above, should also be considered serious.

An 'adverse reaction' is an untoward or unintended response to an investigational medicinal product (IMP) related to any dose administered.

A 'suspected unexpected serious adverse reaction' (SUSAR) is a severe adverse reaction, the nature of which is not consistent with the applicable product information.

# **18.2 Expected adverse reactions**

### 18.2.1 Expected side effects of the termination procedure

Some degree of abdominal pain and vaginal bleeding is expected during and after a medical or surgical termination of pregnancy. Major complications are uterine perforation, pelvic sepsis and haemorrhage (requiring blood transfusion).

### 18.2.2 Expected adverse reactions to misoprostol

Misoprostol may cause diarrhoea, abdominal pain, nausea, vomiting, headache, dizziness and, more rarely, chills and fever.

Uterine bleeding, sometimes heavy and prolonged, may occur.

Very frequent uterine contractions are observed in the hours following prostaglandin intake.

### 18.2.3 Expected adverse reactions to mifepristone

Refer to appendix A, Summary of Product Characteristics.

## **18.3 Protocol specifications**

For the purposes of this protocol all non-serious adverse drug reactions and serious adverse events will be recorded.

The incidence of nausea, vomiting, diarrhoea, dizziness, abdominal pain and bleeding will be recorded following explicit questioning, all other adverse drug reactions will be recorded as AEs.

The following are expected serious adverse events which are being explicitly recorded during the study: emergency admissions for incomplete abortion, missed abortion, or ongoing pregnancy (all of which require surgical evacuation) and pelvic infection without retained products of conception. These events will not be considered SAEs for reporting purposes, as described below.

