# **12.1 General information**

Termination of pregnancy (TOP) is the commonest gynaecological procedure. It can be performed surgically or medically as described in section 1 (Background).

Vaginal bleeding and mild abdominal pain are normal post surgical and medical procedure. Nausea, vomiting and diarrhoea may also be experienced. There is also a risk of infection. Pain relief and antibiotics are provided as part of normal care [7]. Occasionally abortion is incomplete and surgical evacuation is required. Major complications of surgical termination are rare, but include uterine perforation, pelvic sepsis and haemorrhage.

Misoprostol is widely used in the UK to induce medical abortion and in cervical preparation for surgical termination, even though this is an unlicensed indication. Therefore for the purposes of this study misoprostol will be treated as an investigational medicinal product (IMP).

The Summary of Product Characteristics for mifepristone is included in the appendices. This will be prescribed and administered as per normal practice.

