### Surgical termination

Women will be admitted to the Surgical Day Unit where they will receive misoprostol  $400\mu$ g vaginally 3 hours prior to the estimated time of surgery [7]. Following induction of general anaesthesia and mechanical dilatation of the cervix, the uterus will be evacuated using vacuum aspiration with a 9-12 mm curette.

In the absence of excessive bleeding or other problems, women will be discharged 1-2 hours after the procedure.

In line with RCOG recommendations [7], surgical termination will only be performed after 6 weeks' gestation because of the high failure rate (relative risk 2.9 at very early gestations). The appointment for surgical termination will be timed in line with this recommendation.

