### **Medical termination**

At an initial appointment participants will be given mifepristone 200mg orally on the Gynaecological ward by the nursing staff. After 36-48 hours, they will be admitted to the Gynaecological ward where they will receive misoprostol 800µg vaginally at approximately 8:30 a.m.

Following administration of misoprostol, participants will receive oral paracetamol (500mg) plus dihydrocodeine (10mg) or diclofenac (75mg), or parental diamorphine (5mg) as required and as per normal practice.

At the time of the termination participants will receive rectal metronidazole (1g), followed by oral doxycycline (200mg) daily for 7 days, commencing on the day of the termination.

In the absence of excessive bleeding, participants will be discharged 1-2 hours after passage of the uterine contents.

Subsequent management will depend on gestation period:

Less than 9 weeks

• If the contents of the uterus have not been passed 4 hours after misoprostol administration,

a second dose of misoprostol (400µg) will be administered vaginally or orally (depending on preference and amount of bleeding) [7].

• Subsequently, if abortion does not occur and bleeding is not excessive, women will be routinely discharged between 4:30 & 5:00 p.m. The abortion occurs at home and women return for follow-up after 2 weeks.

9 to 13 weeks

- If the contents of the uterus have not been passed 3 hours after misoprostol administration, further doses of misoprostol (400µg) will be given vaginally (or orally if bleeding is heavy) at 3 hour intervals up to a maximum of 4 further doses [7].
- If the contents are still not passed, an ultrasound scan will be performed. In cases of an ongoing pregnancy, missed or incomplete abortion, surgical evacuation will be performed.

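### Section 18.3 gives a minor mechanical harm of dilatation or aspiration no adverse-event entry, while minor drug reactions are recorded

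*Protocol*

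**What the plan says.** Section 18.3 of the protocol states what is to be recorded: "For the purposes of this protocol all non-serious adverse drug reactions and serious adverse events will be recorded". It then lists six symptoms that are asked about explicitly (nausea, vomiting, diarrhoea, dizziness, abdominal pain and bleeding) and adds that "all other adverse drug reactions will be recorded as AEs".

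Section 18.1 defines an adverse event broadly, with no causal link required. It defines an adverse reaction narrowly: it "is an untoward or unintended response to an investigational medicinal product (IMP) related to any dose administered". It also lets medical judgement upgrade an event to serious. An important event that "may require intervention to prevent one of the other outcomes listed in the definition above, should also be considered serious".

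Section 12.1 names misoprostol as the IMP and says of mifepristone: "This will be prescribed and administered as per normal practice".

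Section 12.2 describes the operation: "Following induction of general anaesthesia and mechanical dilatation of the cervix, the uterus will be evacuated using vacuum aspiration". Women having surgery also receive misoprostol 400 µg beforehand. For medical termination at 9 to 13 weeks, if the contents are not passed after the repeat doses, a scan is done: "In cases of an ongoing pregnancy, missed or incomplete abortion, surgical evacuation will be performed".

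The table of events in section 9 schedules adverse events at the procedure, at 2 weeks and at 3 months. Section 14.1 has all women asked about adverse events at both follow-ups.

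**The concern.** The trial compares a mainly drug-based method with an operation, but its rule for non-serious events is worded as it would be for a drug trial. A minor drug effect outside the six symptoms enters the record; section 18.2.2 names headache, chills and fever for misoprostol. A minor injury caused by dilating the cervix or by the curette does not, because no drug caused it.

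The omission is lopsided. Drug reactions can occur in all four groups, since surgical women also receive misoprostol. Mechanical harm arises in the surgical groups and, in the medical groups, only in women who go on to surgical evacuation. A table of other non-serious events by group would therefore show the drug effects of both methods but leave out a kind of harm belonging almost wholly to one of them.

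What sites record is fixed by the protocol. An analysis plan can choose how to tabulate events, but it cannot tabulate what was not collected.

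**Working it through.** No arithmetic applies, because the protocol gives no figure for these events. The check is to follow one event through every route by which the protocol could capture it.

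Take a minor cervical injury at dilatation that is noticed and needs nothing further. The example is illustrative; the protocol does not name it.

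| Route | Where | Captures the event? |
|---|---|---|
| Serious by the listed criteria | 18.1 | No: no death, threat to life, hospitalisation or lasting disability |
| Serious by medical judgement | 18.1 | No, if it neither endangers the woman nor needs intervention to prevent a serious outcome |
| Solicited symptom | 18.3, 14.1 | Only if it shows as one of the six symptoms, and then as the symptom, not the injury |
| Other non-serious event | 18.3 | No: limited to drug reactions |
| Emergency admission | 15.1, clinical effectiveness | Only with an unplanned overnight stay, or an emergency assessment or admission after discharge |
| Visits elsewhere | 14.1 | Only if it leads to another hospital or the GP |
| Cost data | 15.1, cost effectiveness | Only if it leads to an additional intervention or appointment, and then as resource use |

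An event that meets none of these conditions has no adverse-event entry. The same table shows that the class is small, because several routes must all fail.

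Next, does wider wording elsewhere override the rule?

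1. The definition in 18.1 is broad, but a definition says what an adverse event is, not which ones are recorded. Section 18.3 says which are recorded, expressly for this protocol.
2. The table of events has a row for adverse events without saying which qualify.
3. The questioning in 14.1 is general, but its stated purpose is to pick up admissions and visits elsewhere.

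These passages conflict with 18.3 without displacing it.

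Last, does the protocol regard the procedure as a cause of harm? It does. Section 18.2.1 lists expected side effects of the procedure, and the SAE report in 18.4 asks for causality to the procedure, medical or surgical, as well as to either drug. The procedure is thus a recognised cause for serious events, but not under the recording rule for non-serious ones.

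On size, the background section puts major complications of vacuum aspiration at 0.2% to 0.9%, and women returning with post-abortion symptoms at up to 5%. Neither figure can be used. Major complications would be expected to qualify as serious, and women who return to hospital are largely caught by the emergency-admission outcome or by the questions about visits. No rate for minor operative injury is given.

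**The case against.** The strongest reply is that nothing planned depends on these events. Section 15.1 compares acceptability, rating and psychological scales, willingness to pay, emergency admission and particular symptoms; it has no comparison of other non-serious events. Section 14.1 also gives a reason for its choice: emergency admission should take in women with significant procedure-related morbidity. Leaving trivial operative findings aside can be defended as proportionate. All of this stands, and it keeps the severity low.

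It is also fair that the wider wording in 18.1, section 9 and 14.1 may lead staff to record such events anyway, and that an injury written in the operative notes could be looked up later: the protocol already abstracts concomitant medication from the medical notes and verifies serious events against medical records. So the loss is neither certain nor always permanent. But looking up notes afterwards is not a planned step, and staff who follow 18.3 as written would not make the entry.

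Three stronger readings are tempting and are not supported.

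- A reader might infer that non-serious mifepristone reactions are excluded too, because only misoprostol is named as the IMP and 18.1 ties a reaction to an IMP. That is strained. Section 18.3 speaks of drug reactions, 18.2.3 points to the expected reactions to mifepristone, and the SAE report asks for causality to it. Anaesthetic reactions are less clear, since neither 18.2 nor the report names anaesthesia.
- A reader might want a count of lost events. Any rate would be invented.
- A reader might infer that the comparison of the two methods is biased. The planned outcomes do not use these data.

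**Conclusion.** The point holds as a low-severity flaw in the harms record. Section 18.3 as written gives no adverse-event entry to a minor mechanical harm of dilatation or aspiration that escapes every other route, while it records minor drug reactions in all groups. The direction is clear: any by-group summary of other non-serious events would under-record operative harm. The class is small, and the size of the shortfall cannot be stated from the protocol.

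This rests on two assumptions: that staff follow 18.3 as the governing rule, and that someone will at some point tabulate other non-serious events by group. The primary outcome, emergency admission and the symptom comparisons are unaffected.

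**What to change.** Replace the first sentence of section 18.3 with:

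*In all four groups, all non-serious adverse events judged related to the termination (procedure, anaesthesia, mifepristone or misoprostol), and all serious adverse events, will be recorded.*

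Bring the later clause on other drug reactions into line. Use the causality categories already in the SAE report, with anaesthesia added, and tabulate by group. Naming the four causes also settles whether anaesthetic reactions are included.

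The cost is one sentence, one causality field on the adverse-event form and slightly more data entry. No new visit or questioning is needed, since adverse events are already scheduled at the procedure, 2 weeks and 3 months. One weakness remains: causality would be judged by staff who know which method the woman had.
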